2. Duration of Response (DOR), defined as time from the date of the first observed PR/CR to the date of the first subsequent documented disease progression or relapse per IWG 2006 criteria, or death from any cause.
3. Progression Free Survival (PFS), for patients with at least a PR, defined as time from the date of the first dose of study treatment to the date of the first documented disease progression or relapse per IWG 2006 criteria, or death from any cause.
4. Overall Survival (OS), defined as time from the date of the first dose of study treatment to the date of death from any cause.
5. Event-Free Survival (EFS) defined as the number of days from the date of the first dose of study drug to the date of earliest disease progression or death of any cause.
6. Rate of bone marrow blast response, defined as the proportion of patients with a reduction in bone marrow blast counts following treatment.
7. Time to AML transformation, defined as time from first treatment dose to the first date in which AML is established.
8. CR Rate, defined as the proportion of participants who achieved a CR per the IWG 2006 Criteria.
9. Rate of HI, defined as the proportion of patients reaching a HI per the IWG 2006 Criteria.

For AML patients:

1. Overall response rate (ORR) including; CR and CRi according to the Diagnosis and Management of AML in Adults: 2017 ELN Recommendations from an International Expert Panel Revised (see Appendix 12) (Döhner et al., 2017)
 - a. CR is defined as bone marrow blasts < 5%; absence of circulating blasts and blasts with Auer rods; absence of extramedullary disease; ANC $\geq 1.0 \times 10^9/L$ (1000/ μ L); platelet count $\geq 100 \times 10^9/L$ (100 000/ μ L)
 - b. CRi is defined as all CR criteria except for residual neutropenia (< $1.0 \times 10^9/L$ (1,000/ μ L)) or thrombocytopenia (< $100 \times 10^9/L$ (100,000/ μ L)).
2. Duration of Response (DOR), defined as time from the date of the first observed CR/CRi to the date of the first subsequent documented disease progression or relapse per IWG 2006 criteria, or death from any cause.
3. Progression Free Survival (PFS) for patients with at least CRi, defined as time from the date of the first dose of study treatment to the date of the first documented disease progression or relapse per IWG 2006 criteria, or death from any cause.
4. Overall Survival (OS) defined as time from the date of the first dose of study treatment to the date of death from any cause.

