10.2 Efficacy Endpoints

Efficacy will be evaluated by the investigator according to the 2006 IWG response criteria in MDS and for AML according to AML in Adults: 2017 ELN Recommendations from an International Expert Panel Revised (Döhner et al., 2017).

The analyses for efficacy will be performed for the following endpoints.

Overall Response Rate

The proportion of subjects with overall response ($OR = CR + mCR + PR + HI$) will be calculated. The 95% confidence interval for OR rate based on binomial distribution will be constructed.

Complete Remission Rate

The proportion of subjects with complete remission (CR) will be calculated. The 95% confidence interval for CR rate based on binomial distribution will be constructed.

Marrow Complete Remission Rate

The proportion of subjects with mCR with or without hematological improvement will be calculated. The 95% confidence interval for mCR rate based on binomial distribution will be constructed.

Partial remission (PR)

The proportion of subjects with PR with or without hematological improvement will be calculated. The 95% confidence interval for PR rate based on binomial distribution will be constructed.

Hematologic Improvement

The proportion of subjects with HI (erythroid/platelet/neutrophil responses) will be calculated. The 95% confidence interval for the rate of HI based on binomial distribution will be constructed.

Time to AML Transformation

Time to AML transformation will be defined as the number of days from the date of the first dose of study drug to the date of documented AML transformation. AML transformation will be defined as the presence of blast count $\geq 20\%$ in either the peripheral blood or bone marrow. Time to AML transformation will be summarized as median (range). Subjects who do not show transformation to AML will not be included in the analysis.

Duration of Response

Duration of response (DOR) will be defined as the number of days from the date of first response (CR, mCR, PR or HI) to the earliest documentation of progressive disease (PD). Duration of response will be analyzed by Kaplan-Meier methodology. Median DOR will be calculated and 95% confidence interval for median DOR will be presented.

If the response is still ongoing at the time of analysis, the subject's data will be censored at the date of the subject's last available disease assessment. For subjects who never experience a response, the subject's data will not be included in the analysis.

Overall Survival

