Overall survival (OS) will be defined as the number of days from the date of the first dose of study drug to the date of death. Overall survival will be analyzed by Kaplan-Meier methodology. Median OS will be calculated and 95% confidence interval for median OS will be presented. Data from subjects that are alive at the time of analysis will be censored at the date of last study visit or the last known date the subject was alive, whichever is later.

Progression-Free Survival

Progression-free survival (PFS) will be defined as the number of days from the date of the first dose of study drug to the date of earliest disease progression or death due to disease progression or febrile neutropenia. Progression-free survival will be analyzed by Kaplan-Meier methodology. Median PFS will be calculated and 95% confidence interval for median PFS will be presented. All events of disease progression will be included regardless whether the event occurred while the subject was taking the study drug or had previously discontinued the study drug. Refer to Appendix 11 and 12 for the definition of disease progression. If the subject has not experienced disease progression or death, the subject's data will be censored at the date of last disease assessment. Data for subjects without any disease assessments performed after the first dose of study drug will be censored at the time of the first dose of study drug.

Event-Free Survival

Event-free survival (EFS) will be defined as the number of days from the date of the first dose of study drug to the date of earliest disease progression or death of any cause.

Event-free survival will be analyzed by Kaplan-Meier methodology. Median EFS will be calculated and 95% confidence interval for median EFS will be presented. All events of disease progression will be included regardless whether the event occurred while the subject was taking the study drug or had previously

discontinued the study drug. If the subject has not experienced disease progression or death, the subject's data will be censored at the date of last disease assessment. Data for subjects without any disease assessments performed after the first dose of study drug will be censored at the time of the first dose of study drug.

Safety assessments

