24.11.9 Survival

Endpoints:

Overall: death from any cause

Event free: failure or death from any cause

PFS: disease progression or death from MDS

DFS: time to relapse

Cause-specific death: death related to MDS

To convert hemoglobin from grams per deciliter to grams per liter, multiply grams per deciliter by 10.

MDS indicates myelodysplastic syndromes; Hgb, hemoglobin; CR, complete remission; HI, hematologic improvement; PR, partial remission; FAB, French-American-British; AML, acute myeloid leukemia; PFS, progression-free survival; DFS, disease-free survival.

*Dysplastic changes should consider the normal range of dysplastic changes.

‡In some circumstances, protocol therapy may require the initiation of further treatment (eg, consolidation, maintenance) before the 4-week period. Such patients can be included in the response category into which they fit at the time the therapy is started. Transient cytopenias during repeated chemotherapy courses should not be considered as interrupting durability of response, as long as they recover to the improved counts of the previous course.

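### Sections 9.1 and 10.2 of the protocol contradict each other on PFS and DOR, and the time-to-AML rule in 10.2 analyses only patients who transformed

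*Protocol*

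**What the plan says.** **PFS.** Section 9.1 (MDS, item 3) reads "Progression Free Survival (PFS), for patients with at least a PR, defined as time from the date of the first dose of study treatment". The AML item has the same form: "Progression Free Survival (PFS) for patients with at least CRi". Both end at progression, relapse or death from any cause. Section 10.2 names no responder restriction and runs from first dose to the "date of earliest disease progression or death due to disease progression or febrile neutropenia". It censors patients with neither progression nor death at their last disease assessment. Section 10.2 also places all efficacy analyses on the full analysis set, meaning every included patient. Appendix 11 (24.11.9) lists "PFS: disease progression or death from MDS".

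**DOR.** Section 9.1 starts at PR/CR in MDS and CR/CRi in AML, and ends at progression, relapse or any death. For AML the wording is "first observed CR/CRi to the date of the first subsequent documented disease progression or relapse per IWG 2006 criteria", the IWG 2006 criteria being the MDS criteria. Section 10.2 starts at CR, mCR, PR or HI and runs "to the earliest documentation of progressive disease (PD". It censors ongoing responses at the last disease assessment.

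**Time to AML.** Section 10.2 reports a median and range and adds: "Subjects who do not show transformation to AML will not be included in the analysis". Transformation means blasts of 20% or more in blood or marrow.

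**EFS.** Sections 9.1 and 10.2 agree: progression or death of any cause, from first dose.

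**The concern.** Two analysts, one following 9.1 and one following 10.2, would report PFS for different populations with different events, and DOR from different starting points with different events. The trial is open-label and uncontrolled, and response is assessed by the investigator, so a choice made after the data are seen would be hard to defend.

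Neither PFS version is sound alone. Section 9.1 selects patients on something that happens after the clock has started. Section 10.2 leaves out deaths such as those from GVHD, or from infection without febrile neutropenia. These matter here: section 2 cites acute and chronic GVHD in 37% and 17% of patients given azacitidine with DLI.

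The time-to-AML rule selects on the outcome. Its median describes when transformation happened among those who transformed. It does not describe how likely transformation was.

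**Working it through.** The protocol states no figure for these endpoints, so there is none to reproduce. The definitions compare as follows.

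| | 9.1 | 10.2 |
|---|---|---|
| PFS population | at least PR (MDS) or CRi (AML) | no restriction; FAS |
| PFS deaths | any cause | progression or febrile neutropenia only |
| DOR start | PR/CR (MDS), CR/CRi (AML) | CR, mCR, PR or HI |
| DOR end | progression, relapse, any death | PD only |
| AML criteria | IWG 2006 | ELN 2017; Appendices 11 and 12 for progression in PFS |

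The sizes below assume constant hazards. The medians and the shares of other-cause deaths are assumptions, because the protocol gives none.

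**1. PFS in 9.1.** Response is first scheduled after cycle 4, and a cycle lasts 28 days (section 6.1): 4 × 28 = 112 days. With an assumed all-patient median of 6 months, the median among those event-free past day 112 is 6 + 112/30.44 = 9.7 months, before any effect of response itself. At the protocol's 30-50% response rates, only 30 × 0.3 = 9 to 30 × 0.5 = 15 of the 30 phase II patients would enter the analysis.

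**2. PFS in 10.2, if other-cause deaths are censored.** Take a progression-only median of 9 months, so λ₁ = ln 2/9. Let d be the probability of other-cause death by 12 months, so λ₂ = −ln(1 − d)/12.
- Reported 12-month PFS: exp(−12λ₁) = 0.397.
- With every death counted: 0.397 × (1 − d) = 0.357, 0.317 and 0.278 for d = 0.1, 0.2 and 0.3.
- Medians, ln 2/(λ₁ + λ₂): 8.1, 7.2 and 6.5 months, against 9.0 reported.

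**3. DOR.** If a fraction f of first events are deaths that are censored, the median is inflated by 1/(1 − f). An any-cause median of 6 months reads 6.7 at f = 0.1 and 8.6 at f = 0.3. Relapse can also be missed. Suppose an AML patient with 25% blasts at baseline reaches CR and returns to 15%. Appendix 12 calls this relapse (blasts ≥ 5%). Its marrow criterion for PD needs at least a 15-point rise over baseline, here to 40%. Under 10.2 read literally, DOR would not end on that marrow. CRi, which starts DOR for AML in 9.1, is absent from the 10.2 list.

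**4. Time to AML.** Take a window of 18 months (12 of treatment plus 6 of follow-up, synopsis), true median T, λ = ln 2/T and no competing death. The proportion transforming is F = 1 − exp(−18λ). The median among transformers is −ln(1 − F/2)/λ.

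| True median (months) | Transform by 18 months | Median, transformers only (months) |
|---|---|---|
| 12 | 65% | 6.8 |
| 24 | 41% | 7.8 |
| 48 | 23% | 8.4 |
| 96 | 12% | 8.7 |

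An eightfold change in the true median moves the planned summary by about 2 months.

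**The case against.** The strongest defence is that little hangs on these definitions. PFS and DOR are secondary, and time to AML is not even in the section 5.2 list. The two-stage decision uses response alone, OS and EFS count all deaths, deaths on study are tabulated, and GVHD is an endpoint in its own right. All of that stands. It limits the weight of the point but does not remove the contradictions. Section 10.2 lets a later analysis plan record deviations from its descriptions, but it does not say which of two conflicting protocol definitions is the starting point.

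A reader might infer more than the text supports:
- *That DOR ignores death throughout.* It does not. Section 9.1 counts any death for both MDS and AML; 10.2 and the Appendix 11 note on duration of response do not name it.
- *That 10.2 censors other-cause deaths.* It does not say so. Its PFS censoring rule covers patients with neither progression nor death, and its DOR rule covers ongoing responses. Such deaths have no rule, so the inflation is conditional.
- *That 9.1 guarantees 112 event-free days.* Section 8.9 allows unscheduled marrows, and Appendix 11 progression can rest on haemoglobin or transfusion dependence alone. The selection on response remains, but the figure is approximate.
- *That Appendix 11 supplies a third operative PFS definition.* Its line belongs to the IWG criteria, and 10.2 refers to the appendices only to define progression. The working conflict is 9.1 against 10.2.
- *That the relapse example is also missed under 9.1.* This is not established. IWG relapse can be met on blood counts, and IWG progression may be met if the blast band is read from the current level.

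**Conclusion.** The point holds as an inconsistency in the protocol's own text, together with one rule in 10.2 that is wrong as written. PFS and DOR cannot satisfy both 9.1 and 10.2. Each PFS version has its own fault: selection on response from a first-dose clock in 9.1, and restricted causes of death in 10.2. Section 9.1 judges AML relapse and progression by the MDS criteria, against the ELN rule in 10.2. The time-to-AML summary does not measure transformation risk, and that does not depend on any assumption about deaths.

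The sizes are illustrations. The overstatement of 12-month PFS by about 4 to 12 percentage points (40% against 36% to 28%) needs censoring of other-cause deaths, constant hazards, a 9-month progression-only median and 10-30% other-cause deaths at 12 months. It would be tempting to say that treatment-related deaths disappear from the trial's results. They do not, because OS and EFS retain them. The phase II conclusion on response is untouched. The correction should be made, but it is not critical to the trial's primary result.

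**What to change.** - **PFS.** Use one definition in 9.1 and 10.2: all treated patients, from first dose to progression or relapse (Appendix 11 for MDS, Appendix 12 for AML) or death from any cause. Delete the responder restriction and the cause-of-death limit, and mark the line in 24.11.9 as not operative. This PFS nearly equals EFS as written, so keep one of the two or state how they differ. Adding failure from Appendix 11 to EFS would not separate them, since failure there is death during treatment or progression, and it has no AML counterpart.
- **DOR.** Use one definition ending at relapse, progression or death from any cause, with Appendix 12 for AML and a single stated set of starting responses for each disease.
- **Time to AML.** Analyse all MDS patients with less than 20% blasts at baseline, because entry allows marrow blasts up to 30% and some patients could meet the transformation threshold on day 1. Report cumulative incidence with death as a competing event. Censor patients alive without transformation at their last assessment, and delete the exclusion sentence.

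The cost is wording in 9.1, 10.2 and 24.11.9. Dates of death and disease status are already collected (section 8.7). PFS and DOR may be reported as somewhat shorter.

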8.10 Bone Marrow Aspirate

Please see the visit schedule (Appendix 1) specific assessment timepoints for Bone Marrow Aspirate collection. For MDS patients' CR or PR need to be confirmed at least 28 days after the BM evaluation by assessing the stability of improved counts on PB according to the IWG criteria; the need for an additional marrow confirmatory specimen is not required.

The importance of timely and complete disease assessments (including BM and PB assessments) at screening and during the study, whenever clinically indicated, cannot be understated. Failure to perform any of the required disease assessments will result in the inability to determine disease status for that time point and have the potential to weaken the conclusions of this study.

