- h CBC w/diff and platelet count should be completed weekly for the first 2 Cycles and then at the start of each subsequent Cycle. A sample collected on day 28 does not need to be repeated on day 1 of the next Cycle if the 2 Visits are within 72 hours of each other.
- i Complete chemistry panels should be performed within 48 hours of study initiation and then weekly in the Cycle 1 and 2, and bi-weekly at the start of each subsequent Cycle. A sample collected on Day 28 does not need to be repeated on Day 1 of the next Cycle if the 2 Visits are within 72 hours of each other. The panel includes sodium, potassium, chloride, carbon dioxide, BUN, creatinine, magnesium, calcium, phosphorus, glucose, total protein, albumin, AST, ALT, uric acid, lactate dehydrogenase (LDH), alkaline phosphatase and total/direct bilirubin at the beginning of each Cycle.
- j Female subjects of childbearing potential must have negative results for pregnancy test performed at Screening with a serum sample obtained within 14 days prior to the first study drug administration, and prior to dosing with urine sample obtained on Cycle 1 Day 1, if it has been > 7 days since obtaining the serum pregnancy test results. Female subjects who are not of childbearing potential at Screening do not require pregnancy testing.
- k Every 2 cycles.
- l Bone marrow aspiration (BMA) should be conducted prior to study initiation and then after 4, 6 and 8 cycles of AZA + VENETOCLAX and at the end of study or Premature termination. BMA collected on Day 0 of cycle 1 will be for correlative, morphologic and cytogenetic sampling. The other BMA will be for response assessment. Cytogenetics should be repeated in case of abnormal findings at baseline.

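### The last censoring sentence for PFS and EFS in Protocol section 10.2 makes no exception for death and so contradicts the EFS event definition

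*Protocol*

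**What the plan says.** Section 10.2 of the protocol runs EFS from first dose "to the date of earliest disease progression or death of any cause"; section 9.1 gives the same EFS definition for MDS and for AML. PFS in section 10.2 is narrower: its event is the "earliest disease progression or death due to disease progression or febrile neutropenia".

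Each of the two paragraphs then carries the same pair of censoring sentences. The first is conditional: "If the subject has not experienced disease progression or death, the subject's data will be censored at the date of last disease assessment". The second is not: "Data for subjects without any disease assessments performed after the first dose of study drug will be censored at the time of the first dose".

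On timing, footnote l of Appendix 1 places the marrow after baseline "then after 4, 6 and 8 cycles of AZA + VENETOCLAX and at the end of study or Premature termination". Section 8.10 includes both bone marrow and peripheral blood among disease assessments. The protocol does not say which of these is enough for the censoring rule.

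**The concern.** A patient who dies before any post-dose disease assessment meets the EFS event definition and also meets the day-0 censoring rule. The definition makes the patient an event on the date of death. The rule makes the same patient a non-event who never enters the risk set. Section 10.2 does not say which prevails.

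The patients exposed are not a random subset. A patient who stops treatment alive is due end-of-study procedures, including a marrow, whereas a patient who dies suddenly on treatment is not assessed again. The literal rule therefore selects early deaths, and the error can go in only one direction: EFS looks better than it is. In a single-arm, open-label trial of a drug added to a myelosuppressive backbone, a choice that can only favour the treatment should not be left to whoever programs the analysis.

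**Working it through.** The protocol states no EFS or PFS rate, median or event count, so there is no figure to reproduce. The check has three parts.

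**1. The text, for a patient who dies before any post-dose assessment**

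| Statement in section 10.2 | Result |
|---|---|
| EFS definition | event on date of death |
| First censoring sentence | does not apply, because the patient died |
| Second censoring sentence | applies; censored at first dose |
| PFS definition | event only if death is due to progression or febrile neutropenia |

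For EFS, the first and third rows contradict each other. For PFS they do so only for the two named causes of death.

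**2. How long a patient can be at risk without an assessment**

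- If only the scheduled response marrow counts: 4 × 28 = day 112, or 4 × 42 = day 168 if every cycle is delayed as section 6.1 allows.
- If the marrow chimerism sample counts (Appendix 1, every 2 cycles): about 2 × 28 = day 56.
- If a blood count counts: about day 7, since counts are weekly in cycles 1 and 2.

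**3. Size of the effect**

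*Direct Kaplan-Meier arithmetic.* Take n patients, k deaths before any assessment and m later events, with no other censoring. Survival is (n − k − m)/n if the deaths are events, and (n − k − m)/(n − k) if they are censored at day 0. Here n = 30 (the phase II size); m = 9 and all values of k are assumed.

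| k | Deaths as events | Day-0 censoring | Difference (points) |
|---|---|---|---|
| 1 | 20/30 = 66.7% | 20/29 = 69.0% | 2.3 |
| 3 | 18/30 = 60.0% | 18/27 = 66.7% | 6.7 |
| 6 | 15/30 = 50.0% | 15/24 = 62.5% | 12.5 |
| 9 | 12/30 = 40.0% | 12/21 = 57.1% | 17.1 |

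*Exponential illustration.* Let M be the true median and w the window in days. The share of events inside the window is F = 1 − 2^(−w/M). If a fraction s of these are deaths without an assessment, q = s × F is censored at day 0. After the window, survival is then reported as S/(1 − q). Assume M = 183 days, so true 6-month EFS is 0.50.

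- w = 112: F = 1 − 2^(−112/183) = 0.346.
  - s = 0.25: q = 0.086; 0.50/0.914 = 0.547, or +5 points. Median about 6.8 months.
  - s = 0.50: q = 0.173; 0.50/0.827 = 0.605, or +10 points. Median about 7.6 months.
- w = 7: F = 1 − 2^(−7/183) = 0.026.
  - s = 0.50: q = 0.013; 0.50/0.987 = 0.507, or +0.7 points. Median about 6.1 months.

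*What drives the result.* With w = 112 and s fixed at 0.50, true medians of 120, 183 and 270 days give +0.11, +0.10 and +0.09. Varying s from 0.25 to 0.75 over the same medians gives +0.04 to +0.19. The assumed share of deaths and the window matter; the median hardly does.

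**The case against.** The strongest reply is that the two censoring sentences belong together. The first limits censoring to subjects without progression or death, and the second only supplies a date when no last assessment exists. The EFS definition, the full analysis set of all included patients and the intent-to-treat basis in section 10.2 all support that reading. This stands as a sensible interpretation, and a careful statistician might well adopt it. But the second sentence does not carry the limit over, and the paragraph can be followed to the letter with the opposite result.

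Three stronger readings are tempting, and the documents do not support them.

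- *That all deaths up to the cycle 4 marrow are lost.* This needs disease assessment to mean the response marrow alone. Section 8.10 includes peripheral blood, and Appendix 11 allows MDS progression to be called on counts. Even with marrow required, a chimerism sample falls at about day 56, and a marrow is due at premature termination. Day 112 is one end of the range.
- *That early mortality is hidden.* OS counts every death from first dose without this rule, and section 10.2 tabulates deaths on study.
- *That PFS suffers as EFS does.* Under section 10.2 most other deaths are not PFS events in any case. Section 9.1 restricts PFS to responders, who have been assessed by definition, so the rule cannot act there.

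**Conclusion.** The point holds as an unresolved contradiction in section 10.2, not as a settled exclusion of early deaths. Read literally, the last sentence turns an EFS event into a day-0 censoring, and the bias can only be upward.

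The size cannot be fixed from the protocol, which gives neither an early-death rate nor a definition of disease assessment. It runs from negligible if blood counts qualify to about 5 to 10 points of 6-month EFS if only the response marrow does. The upper figures assume exponential event times, a 6-month median, and 25 to 50% of events before day 112 being deaths without a marrow.

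Only secondary endpoints are touched. The primary response rate and the two-stage rule do not change. The correction is still worth making because the rule is stated in the protocol, is simple to repair, and otherwise leaves open a choice that can only flatter the result.

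**What to change.** Replace the last censoring sentence in both the PFS and the EFS paragraph of section 10.2 with:

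*Subjects who are alive and progression-free and have no disease assessment after first dose are censored at first dose; a death that meets the event definition is an event on its date whether or not a disease assessment was done.*

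State in the same place whether peripheral blood counts alone are a disease assessment. In the PFS paragraph, also give the censoring date for a patient who dies of a cause that is not a PFS event, since the replacement sentence does not cover that case.

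The cost is a clause in two paragraphs and one definition. No extra visit, sample or patient is needed. Reported EFS and PFS may become slightly less favourable.

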Stable disease	Absence of CR _{MRD-} , CR, CR _i , PR, MLFS; and criteria for PD not met	Period of stable disease should last at least 3 mon
Progressive disease (PD)*, †	Evidence for an increase in bone marrow blast percentage and/or increase of absolute blast counts in the blood: 
 • 50% increase in marrow blasts over baseline (a minimum 15% point increase is required in cases with $< 30\%$ blasts at baseline; or persistent marrow blast percentage of $> 70\%$ over at least 3 mo; without at least a 100% improvement in ANC to an absolute level ($> 0.5 \times 10^9/L$ [$500/\mu L$], and/or platelet count to $> 50 \times 10^9/L$ [$50\,000/\mu L$] non-transfused); or • 50% increase in peripheral blasts (WBC \times % blasts) to $> 25 \times 10^9/L$ ($> 25\,000/\mu L$) (in the absence of differentiation syndrome)†; or • New extramedullary disease 	Category mainly applies for older patient given low-intensity or single-agent “targeted therapies” in clinical trials In general, at least 2 cycles of a novel agent should be administered Some protocols may require blast increase in 2 consecutive marrow assessments at least 4 wk apart; the date of progression should then be defined as of the first observation date Some protocols may allow transient addition of hydroxyurea to lower blast counts

CATEGORY	DEFINITION	COMMENT
		“Progressive disease” is usually accompanied by a decline in ANC and platelets and increased transfusion requirement and decline in performance status or increase in symptoms
Relapse		
Hematologic relapse ¶ (after CR _{MRD-} , CR, CR _i)	Bone marrow blasts ≥ 5%; or reappearance of blasts in the blood; or development of extramedullary disease	
Molecular relapse (after CR _{MRD-})	If studied pretreatment, reoccurrence of MRD as assessed by RT-qPCR or by MFC	Test applied, sensitivity of the assay, and cutoff values used must be reported; analyses should be done in experienced laboratories (centralized diagnostics)

ANC, absolute neutrophil count; IDH, isocitrate dehydrogenase; MLFS, morphologic leukemia-free state; WBC, white blood cell.

*The authors acknowledge that this new provisional category is arbitrarily defined; the category aims at harmonizing the various definitions used in different clinical trials.

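### In AML patients, EFS and the Section 10.2 versions of PFS and DOR do not count hematologic relapse after CR/CRi as an event, so these durations are biased upward

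*Protocol*

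**What the plan says.** **EFS.** Section 9.1 (in both the MDS and the AML list) and Section 10.2 run EFS from first dose "to the date of earliest disease progression or death of any cause". Section 24.11.9 of Appendix 11 has a different rule: "Event free: failure or death from any cause".

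**PFS.** Section 10.2 runs it "to the date of earliest disease progression or death due to disease progression or febrile neutropenia" and points to Appendices 11 and 12 for what progression means. Section 9.1 runs it "to the date of the first documented disease progression or relapse per IWG 2006 criteria, or death from any cause".

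**DOR.** Section 10.2 runs it "to the earliest documentation of progressive disease (PD"; neither relapse nor death is listed. Section 9.1 runs it "to the date of the first subsequent documented disease progression or relapse per IWG 2006 criteria, or death from any cause".

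**AML criteria.** Section 24.12.2 of Appendix 12 has separate rows for progression and relapse. The marrow route to progression is "50% increase in marrow blasts over baseline (a minimum 15% point increase is required in cases with" fewer than 30% blasts at baseline. Hematologic relapse after CR or CRi is "Bone marrow blasts ≥ 5%; or reappearance of blasts in the blood; or development of extramedullary disease".

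**Eligibility.** Section 6.6 admits only patients with marrow blasts below 30%.

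**Censoring.** Under Section 10.2, EFS and PFS are censored at the last disease assessment when there is no progression or death. DOR is censored there when the response is still ongoing.

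**The concern.** Loss of remission is the failure that duration endpoints are meant to capture. If relapse is not an event, a responder whose disease has returned still counts as event-free until progression is met against the study-entry value, or until a death that the definition counts. The error therefore falls on responders and runs one way, towards longer EFS, PFS and DOR. The study has a single arm, so no comparator shares the bias, and readers will set these medians beside outside results.

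**Working it through.** The protocol states no median, event count or power for EFS, PFS or DOR, so there is no figure to reproduce. The check compares the definitions, works out the AML thresholds and then illustrates the size.

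**1. Events by section**

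| Endpoint | Section 9.1 | Section 10.2 | Appendix 11 |
|---|---|---|---|
| EFS | progression, any death | progression, any death | failure, any death |
| PFS | progression, relapse, any death | progression, death from progression or febrile neutropenia | progression, death from MDS |
| DOR | progression, relapse, any death | PD only | progression, or progression/relapse after HI |

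Relapse is absent from EFS everywhere in the body text. For PFS and DOR, Sections 9.1 and 10.2 contradict each other.

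**2. AML marrow threshold for progression**

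For baseline blasts b (%), the threshold is T(b) = max(1.5b, b + 15). Since 1.5b exceeds b + 15 only when b > 30, the 15-point minimum binds for every eligible patient.

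| b | 5 | 10 | 15 | 20 | 25 | 29 |
|---|---|---|---|---|---|---|
| T(b) | 20 | 25 | 30 | 35 | 40 | 44 |
| Points above the 5% relapse limit | 15 | 20 | 25 | 30 | 35 | 39 |

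**3. One patient followed through**

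An AML patient enters at 15%, reaches CR after cycle 4 and shows 12% after cycle 8. Since 12 ≥ 5, this is hematologic relapse. Since 12 < 30, it is not marrow progression. Unless another route is met (new extramedullary disease, or a 50% rise in peripheral blasts to above 25 × 10⁹/L), Section 10.2 gives no EFS, PFS or DOR event. Resetting baseline to the remission marrow would not help: at 2%, T = 2 + 15 = 17, still above 12.

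The event may come late or never. Appendix 1 schedules marrows after cycles 4, 6 and 8 and at end of study or premature termination. The later contacts in Section 8.7 record disease status but schedule no marrow.

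**4. MDS**

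Progression in 24.11.7 already includes a fall of at least 50% in granulocytes or platelets from best response, a hemoglobin fall of at least 2 g/dL, and transfusion dependence. Relapse in 24.11.6 is nearly the same list. What remains includes a hemoglobin fall of 1.5 to under 2 g/dL, and return to pretreatment blasts if progression is read against the entry category.

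**5. Illustration of size (every input is an assumption)**

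*DOR in AML responders.* Time to relapse is exponential with median m months (rate λ₁ = ln 2/m). The further lag to PD is exponential with mean L months (rate λ₂ = 1/L). With PD as the only event, S(t) = [λ₂e^(−λ₁t) − λ₁e^(−λ₂t)]/(λ₂ − λ₁). For m = 6 and L = 3, λ₁ = 0.1155 and λ₂ = 0.3333, and S(9.27) = (0.3333 × 0.3427 − 0.1155 × 0.0455)/0.2178 = 0.50. Simulated medians (400,000 patients):

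| m (relapse counted) | PD only, L = 1 | PD only, L = 4 | Overstatement |
|---|---|---|---|
| 4 | 5.08 | 8.14 | 27% to 104% |
| 6 | 7.05 | 10.30 | 18% to 72% |
| 12 | 12.99 | 16.33 | 9% to 37% |

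*EFS in all patients.* Assume response rate R at 4 months, median 6 months from response to relapse, non-responder median 3 months, and no gap in MDS. With relapse counted, 12-month EFS = R × 2^(−8/6) + (1 − R) × 2^(−12/3).

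- R = 0.5: 0.5 × 0.397 + 0.5 × 0.0625 = 23.0%. With all patients AML and L = 3, S(8) = 0.571, giving 0.5 × 0.571 + 0.031 = 31.6%, about 9 points higher. The median moves from 6.31 to 7.82 months.
- R = 0.3: 0.3 × 0.397 + 0.7 × 0.0625 = 16.3%. With 30% AML and L = 1, the result is 16.7%, about 0.5 points higher. The median moves from 4.86 to 4.93 months.

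Death in remission is not modelled. For EFS, the lag runs to whichever of PD or death comes first.

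**The case against.** The other side has several sound points.

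- A reader might infer that relapse is excluded outright. It is not. EFS counts any death, Section 10.2 PFS counts some deaths, and extramedullary relapse or very high blood blasts meet PD. For EFS the error is confined to the interval from relapse to PD, death or censoring. This stands.
- A reader might apply the fault to the whole trial population. Appendix 11 does not support that, because its progression definition covers most MDS relapse. This stands.
- A reader might infer that Section 10.2 censors a relapsed patient as an ongoing responder for DOR. Its censoring rule covers only a response that is still ongoing. A patient in relapse without PD has no rule at all, which is a gap and not an instruction to censor.
- Section 9.1 already counts relapse for PFS and DOR, so those two are overstated only if Section 10.2 prevails. This stands; for them the fault is a contradiction. For EFS, neither section names relapse.
- The pointer to the appendices sits in the PFS paragraph only, and Section 9.1 judges AML DOR and PFS by IWG 2006. Under 24.11.7, blasts rising from below 5% to above 5% could be progression if read against remission status. But Section 10.2 opens by assigning ELN 2017 to AML, so Appendix 12 is the natural source. The IWG wording does not repair the gap either: its blast criterion for relapse is return to the pretreatment level, which 12% after entry at 15% does not meet.
- These are secondary endpoints summarised by Kaplan-Meier medians. The two-stage rule uses response, and OS is unaffected. This stands and limits the weight of the point.

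**Conclusion.** The point holds for AML. Followed as written, EFS in both sections and PFS and DOR in Section 10.2 give no event at hematologic relapse after CR/CRi unless PD is also met, and every eligible AML patient faces the 15-point minimum. The upward direction follows from the definitions. The size does not: the proportion with AML, the relapse times and the lag from relapse to PD are not in the protocol. Under the assumptions shown, median DOR in AML responders is overstated by 9% to 104%, 12-month EFS by about 0.5 to 9 points, and median EFS by about 0.1 to 1.5 months. No single figure should be quoted as the bias. In MDS the gap is small. It would go too far to infer that the trial's main conclusion is compromised, because the phase II decision rests on response. This should be fixed, but it is not a critical fault.

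**What to change.** - In Section 9.1 (both EFS items) and Section 10.2 (EFS, PFS, DOR), name relapse after response as an event: 24.11.6 and 24.11.10 for MDS, and the hematologic relapse row of Appendix 12 for AML.
- Align the PFS and DOR events in Section 10.2 with Section 9.1. This also brings in death from any cause, as Section 9.1 already has it, and gives DOR a rule for a patient who relapses without PD.
- For AML DOR and PFS in Section 9.1, replace the reference to IWG 2006 with the ELN criteria that Section 10.2 assigns to AML.
- Reconcile EFS with 24.11.9 by stating whether treatment failure is an event.

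The cost is wording. Relapse is judged from assessments already planned, so no new data are needed. The reported durations will be less favourable, so the change should be made before the data are seen.
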